17. Description of procedures to be performed.

The assessment schedule is summarized in Table 1 for screening (phone), baseline (in-person), 6-month assessment visit (in-person), and 12-month (phone) assessments. However, if a dyad prefers to complete the telephone assessments in person (e.g., while they are on station for another appointment), arrangements will be made to accommodate that request.

Table 1. Assessment Schedule

Measure (completed by Veteran or caregiver)	Admin. Time	S	B	6 mo	12 mo
Eligibility Screening (CG)	5m	X			
Dem Serv Mini-Screen (CG)	< 2m	X			
Subjective Stress/ Subjective Health (V, CG)	1m		X	X	X
Demographics (CG, CG*)	< 10m		X		
Health Literacy Screener (CG)	< 2m		X		
MoCA (V)	10m		X		

PSM IADL/ADL (CG*)	10-12m		X		
RMBPC (CG*)	5-10m		X	X	
CSDD (V, CG*)	10-20m		X	X	
Veteran QOL-AD (V, CG*)	5-10m		X	X	X
EuroQoL-5 Domain (V, CG*)	<5m		X	X	
Social Engagement (V, CG*)	<5m		X	X	
Dyadic Adj. Scale (V, CG)	5-10m		X	X	
Mutuality Scale (V, CG)	5m		X	X	X
Zarit Burden (CG)	< 5m		X	X	X
GAD-7 (CG)	< 5m		X	X	X
CES-D (CG)	5m		X	X	X
WHO-QOL-OLD (CG)	3m		X	X	
FFMQ (V, CG)	10m		X	X	X
Desire to Inst. (DTI) (CG)	<5m		X	X	X
NH Placement (EHR, CG)	<1m			X	X
Care Consultation Satisfaction Survey (CG)	<5m			X	
Caregiver Time Burden (min)			<130	<105	<50
Veteran Time Burden (min)			<80	<75	<30

Note. V = measures completed by veteran; CG = completed by caregiver; EHR = extracted from the electronic health record.

Screening

A HIPAA waiver for screening purposes will be obtained. Eligibility screening for interested dyads will typically occur over the telephone. If the Veteran and/or caregiver meets the inclusion criteria and do not meet exclusion criteria, a baseline assessment appointment will be scheduled. Informed consent procedures will be performed at baseline in accordance with the consensus recommendations for research with cognitively impaired populations developed by the Alzheimer's Association³³ and described in detail below. Proxy consent and participant assent will be collected when the participant is willing to assent for the study but is determined by the capacity assessment at the time of consent to be lacking capacity. Caregivers will also complete an informed consent. Veterans and their family caregivers will complete separate consent forms.

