The study team has extensive clinical expertise in the delivery of interventions for individuals with dementia and their caregivers. See CVs and Bios uploaded and attached to this protocol for sample publications by the study team.

20. Description of the anticipated data and how the data will be analyzed to test the specific hypotheses results.

Study Design, Power, & Target Sample Size

We plan to recruit at least 70 dyads across the 3-5 year study period to ensure 50 completers at 6 months. This rate of 2 dyads per month is feasible given that there are 421 veterans with dementia currently receiving services from the TVAMC outpatient clinics (FY2013 clinical data). If 50% of them are in moderate to high distress (a conservative estimate based on our preliminary work), there would be over 200 individuals eligible. Power analyses were conducted to support this sample size (see attached grant text for more details).

Data Management and Analysis

Data Entry:

Data will be entered using Remark Office Optical Mark Recognition software and analyzed using Statistical Package for the Social Sciences (SPSS). Data analysis will be conducted using the VA Informatics and Computing Infrastructure (VINCI) server behind the VA firewall, as has been done for other TVAMC IRB approved studies. The research assistant will review all data for accuracy and will complete data tracking forms. A descriptive analysis of all assessment data will be conducted in order to examine distributional properties and correlations between the measures and the assumptions of statistical tests will be examined. Where necessary and sensible, data transformations, including the elimination of outliers, will be considered for variables with problematic properties.

Treatment of Missing Values:

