Missing values are unavoidable in applied clinical intervention research. Where possible, variables to index the number and reasons for missing values will be documented. Based on the distribution of these missing value indices we may choose to eliminate some participants from the analyses ("list-wise deletion"). The extent that missing values are related to the independent (treatment group) or outcome variables will be assessed and if necessary controlled for statistically. Individuals who complete at least four sessions of the intervention (CC or CC+C) will be included in final analyses when time 2 data are available. Strict intention-to-treat methodologies are too conservative for this relatively small initial pilot study.

Data Analysis:

A series of one-way between subjects analyses of covariance (ANCOVAs) will be used to examine the main effect of “group” on 6 month variables of interest while controlling for values at baseline. The dependent variable in these analyses will be change scores with pre-treatment scores as the covariate. This analysis is statistically equivalent to ANCOVA with pre-treatment scores as the covariate and 6-month scores as the dependent variable, but it has an interpretational advantage in that the change scores represent an individual treatment effect (change during treatment). The change scores also represent the interaction term of a 2 (Group) X 2 (Time) repeated measures ANOVA. Consequently, when other covariates are added to the ANCOVAs to address treatment moderation effects, those covariate effects will be directly interpretable as moderator effects. That is, the added terms will assess the effects of the covariates on changes during treatment irrespective of Group (essentially a Time by Covariate interaction). When the interaction (multiplicative product) of covariate and Group is also added as another term in the ANCOVA, that interaction term will supply the moderating effect of the covariate on change during treatment as function of Group (i.e., differential effect of treatment as a function of the covariate).

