Outcome measures for caregivers will be run in separate analyses from those of the veterans with dementia, such that a series of ANCOVAs are anticipated for 1) self-report measures for the caregiver; 2) self-report measures for the veteran with dementia; and 3) proxy-reported measures for the veteran with dementia (as rated by their caregiver). Partial eta squared statistics of effect will be used as the primary indicator of likely treatment effects in this small sample. A large effect is indicated by a partial eta squared (hp^2) greater than or equal to 0.14, a medium effect is determined by a value greater than or equal to 0.06, and small effects are determined by values greater than or equal to 0.01. For the purposes of the current study, between groups effect sizes greater than or equal to .01 (a small effect) will be interpreted as potentially clinically meaningful in the interpretation of results since two active treatments are being compared. Cohen's d statistics will also be calculated for the purposes of the current feasibility study because they are one of the most common methods of estimating effect sizes and are more easily interpreted than the partial eta squared effects. In order to calculate Cohen's d statistics, standard error terms will be converted into standard deviations and used with the estimated marginal means from the post-treatment ANCOVAs. Both types of effect sizes will be calculated. Finally, logistic regression analyses will be conducted to determine if NH placement at 6 and 12 months is differentially related to treatment condition (i.e., group assignment) for individuals with dementia. NH placement (or not) will be the dependent variable in these analyses, and independent variables will include Group and relevant covariates.

21. Risks (physical, psychological, social, and economic) and steps taken to minimize these risks.

Physical Risks: There are no anticipated physical risks with this study. All activities in the study will be within the normal limits of participants' everyday physical demands. Increased veteran activity and/or range of motion could potentially result in exacerbation

of pre-existing pain conditions (e.g., arthritis, etc.); however, potential benefits in strength/decreased disability exceed potential risks.

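### For outcomes with a baseline covariate, the planned SE-to-SD conversion puts Cohen's d on the ANCOVA residual SD, so a covariate-adjusted index is reported under the plain name

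*Combined protocol and SAP*

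**What the plan says.** Section 20 (Data Analysis) compares the two arms at 6 months by a series of ANCOVAs. "The dependent variable in these analyses will be change scores with pre-treatment scores as the covariate", and the plan notes that using the 6-month score as the dependent variable would be equivalent.

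Two effect sizes are planned. The first is the leading one: "Partial eta squared statistics of effect will be used as the primary indicator of likely treatment effects in this small sample". Its cut-offs are 0.01, 0.06 and 0.14; for the top one, "A large effect is indicated by a partial eta squared (hp^2) greater than or equal to 0.14". Between-group values of .01 or more are to be read as potentially clinically meaningful.

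The second is Cohen's d, added because "they are one of the most common methods of estimating effect sizes and are more easily interpreted than the partial eta squared effects". Its calculation is given in one clause: "standard error terms will be converted into standard deviations and used with the estimated marginal means from the post-treatment ANCOVAs".

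The plan does not define which standard error terms are meant, names no raw SD, and does not call this d adjusted. The documents give no SD and no baseline-to-6-month correlation for any measure. In Table 1 (section 17) most outcome scales are scheduled at both baseline and 6 months. The Care Consultation Satisfaction Survey is scheduled at 6 months only.

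**The concern.** An ordinary between-group d expresses a difference in units of the spread of scores between people. The SE of an ANCOVA estimated marginal mean reflects something smaller: the spread left after the baseline score has explained part of it. An SD recovered from that SE is therefore a residual SD, and dividing by it gives a larger d for the same raw difference.

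The increase depends on how strongly each measure correlates with its own baseline. Two scales with the same raw standardised difference can thus show different d values only because their correlations differ. The satisfaction survey has no baseline score, so its d would be on a raw SD and would sit under the same label as the others.

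What is at stake is interpretation. The plan adds d so that readers have a familiar figure, and section 32 says the results will serve as pilot data for grant proposals. A reader who is not told the SD cannot know whether a reported d may be set beside published d values, or used in a sample-size formula that expects a raw-SD d.

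**Working it through.** The plan states no d, SD or r, so there is no figure of its own to reproduce.

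**Inputs**
- Model: dependent variable is change, covariate is the baseline score (section 20, Data Analysis).
- Sample: 70 dyads recruited "to ensure 50 completers at 6 months" (section 20, Study Design, Power, & Target Sample Size). The allocation ratio is not stated; 25 per arm is assumed.
- r, the within-group correlation of baseline with 6-month score: assumed 0.3, 0.5, 0.7 and 0.8.
- Illustrative true difference: 0.50 raw SDs (assumed), with equal SDs at both times unless stated.

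**Step 1: what the conversion returns.** The SE of the marginal mean in arm j is √[MSE × (1/n_j + (x̄_j − x̄)²/SS_x)]. The second term is the chance baseline imbalance and is small. Hence SE × √n_j ≈ √MSE, the residual SD. In simulation with 25 per arm, the SD recovered this way averaged 1.005 times √MSE.

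**Step 2: change score or 6-month score.** Subtracting the covariate from the outcome alters only the covariate's slope. The group effect and MSE are the same, so the change-score form does not avoid the issue.

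**Step 3: size against the raw 6-month SD.** √MSE ≈ SD_6mo × √(1−r²), so d_plan = d_raw / √(1−r²). The last two columns are simulation means: 20,000 trials per row, normal data, change score as dependent variable.

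| r | √(1−r²) | 1/√(1−r²) | Excess | Mean d, plan's rule | Mean d, raw baseline SD |
|---|---|---|---|---|---|
| 0.3 | 0.954 | 1.048 | 5% | 0.53 | 0.51 |
| 0.5 | 0.866 | 1.155 | 15% | 0.58 | 0.51 |
| 0.7 | 0.714 | 1.400 | 40% | 0.71 | 0.51 |
| 0.8 | 0.600 | 1.667 | 67% | 0.84 | 0.51 |

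At r = 0 the two agree (0.506 and 0.507). A 20/30 split gives the same plan d to within 0.01.

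**Step 4: dependence on the comparator.** With equal SDs, the raw SD of change is SD × √[2(1−r)]. Against that SD the excess factor is √[2(1−r)] / √(1−r²) = √[2/(1+r)], which is 1.240, 1.155, 1.085 and 1.054. The pattern in r reverses, which is one more reason to state the SD.

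**Step 5: partial eta squared.** With equal arms its population value is d²/[d² + 4(1−r²)], where d is on the raw SD. For d = 0.50:
- r = 0: 0.25/4.25 = 0.059
- r = 0.3: 0.25/3.89 = 0.064
- r = 0.5: 0.25/3.25 = 0.077
- r = 0.7: 0.25/2.29 = 0.109
- r = 0.8: 0.25/1.69 = 0.148

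The SE conversion does not touch this index, but it too uses residual variance and rises with r. Inverting, raw d = 2√[η/(1−η)] × √(1−r²). The cut-offs 0.01, 0.06 and 0.14 correspond to raw d of 0.20, 0.51 and 0.81 at r = 0, and to 0.14, 0.36 and 0.58 at r = 0.7.

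**Step 6: direction of change if the baseline SD is used.** A d on the baseline SD is below the plan's d only when SD_6mo/SD_baseline is less than 1/√(1−r²). Take a ratio of 1.2 (assumed) and a difference of 0.50 baseline SDs. The plan's d is 0.5/(1.2 × 0.954) = 0.44 at r = 0.3, 0.5/(1.2 × 0.866) = 0.48 at r = 0.5, and 0.5/(1.2 × 0.714) = 0.58 at r = 0.7. At the two lower correlations it is below 0.50.

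**The case against.** The case for leaving the text alone has weight. The plan discloses that d is built from ANCOVA output. A residual-SD d is a legitimate effect size, and it maps one-to-one onto partial eta squared, the leading index, which is on the same scale. No decision depends on d. The size of the shift is unknown without r. And the term standard error terms is undefined: if SEs of unadjusted means were meant, the recovered SD would be raw.

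Much of this stands. There is no arithmetic error, and the percentages are conditional on r. The alternative reading is weak, however. The clause pairs the standard errors with the estimated marginal means, and raw SDs would need no conversion. Even on that reading the plan would still have to name its SD. Agreement with partial eta squared does not rescue the plain label either, because d was added for its familiarity.

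Some stronger inferences are tempting, and the documents do not support them:
- A reader might infer that the rule makes a positive finding more likely. No test or decision rule uses d. The .01 threshold directly follows the partial eta squared cut-offs and uses that index's small-effect value, so it is not a threshold on d.
- A reader might infer that partial eta squared is free of the issue. Step 5 shows that it also rises with r.
- A reader might infer that every reported d is affected. Measures without a baseline covariate, such as the satisfaction survey, are not.
- A reader might infer that dividing by the baseline SD always lowers d. Step 6 shows that it need not.

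**Conclusion.** The concern holds as a matter of reporting and interpretation, and the text should be changed. For outcomes with a baseline covariate, the stated conversion yields a covariate-adjusted effect size on the residual SD and reports it under the plain name. Against the raw 6-month SD the excess runs from about 5% at r = 0.3 to about 67% at r = 0.8.

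This rests on three assumptions: the standard errors are those of the estimated marginal means; r lies in the assumed range; and the model has the baseline score as its only covariate. Further covariates, as in the moderator models, could shrink the residual SD more. The simulated means also assume normal data and equal SDs at both times.

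The index itself is valid. The fault is that the plan's rule, followed as written, gives values that cannot be set beside ordinary d values or compared across the trial's measures, contrary to the purpose stated for reporting d. No test, threshold or hypothesis is affected.

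**What to change.** In section 20 (Data Analysis), replace the SE-to-SD conversion with a rule of this kind: d is the ANCOVA-adjusted mean difference divided by the raw pooled within-group SD of that measure in the same analysis set, using the baseline SD, or the 6-month SD where the measure has no baseline. State in each table which SD was used. Label partial eta squared, and any residual-SD d that is also reported, as covariate-adjusted.

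The cost is two or three sentences. The raw SDs come from data already to be collected and described (section 20, Data Entry): "A descriptive analysis of all assessment data will be conducted in order to examine distributional properties and correlations between the measures".

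There are two downsides:
- d will usually be smaller than under the current rule. With the baseline SD this is not guaranteed: it fails when SD_6mo/SD_baseline exceeds 1/√(1−r²).
- d will no longer map one-to-one onto partial eta squared. With equal SDs, for example, a d of 0.5 would sit beside a partial eta squared of about 0.11 at r = 0.7 or 0.15 at r = 0.8. One sentence in the report should explain this.

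The plan proposes no confidence interval for d, and this change does not require one.

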Participants assigned to both groups will have: 1) reduced unmet needs, 2) reduced depressive symptoms, and 3) higher levels of satisfaction with care at 6 months than their baseline assessment values.

Caregivers assigned to CC+C will have greater reductions in caregiver burden at 6 months than those assigned to CC alone. Indicators of relationship strain (e.g., marital distress and/or mutuality) will show greater improvement in CC+C than CC at 6 months. 6 month gains in shared pleasant events, social engagement, and quality of life will also be greater in CC+C than in CC alone. 6-month desire to institutionalize will be lower in the CC+C group than those randomized to CC. Treatment engagement (e.g. action plan completion, attendance) is also predicted to be higher in the CC+C group than in CC.

For Aim 3, we anticipate that individuals who receive the CC+C intervention will have lower rates of placement in long-term care facilities at 6 and 12 months than those who receive CC alone. We also expect that behavioral problems will impact treatment outcomes such that those dyads with higher levels of behavioral disturbance at baseline will have greater change scores at 6 months. Spousal relationship to the veteran is also expected to moderate treatment outcome such that spousal caregivers are anticipated to have lower change scores compared to non-spousal caregivers across time; however, we expect this effect to be attenuated in the CC+C condition.

7. Background, including results of relevant research, gaps in the current knowledge.

Scope of the Problem

Over five million Americans are diagnosed with Alzheimer's disease or a related disorder (ADRD) and rates are expected to triple by 2050¹. It is the 6th leading cause of death in the United States and one in three older adults will have dementia when they die².

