Veterans have high rates of known risk factors that place them at increased risk of developing dementia including: PTSD,³ diabetes^{4,5}, substance use disorders,⁶ and cardiovascular disorders.⁷ Over 7% of veterans 65 and over receiving care through the Veteran's Health Administration (VHA) are currently diagnosed with dementia.⁸ In a study of dementia prevalence among VHA system users, [name], [name], and colleagues found that diagnosis by VISN varied between 5.8% to 9.4%.⁸ VISN 7, where the current work is proposed, had the highest dementia rates of any VISN in the country and was in the region with the greatest rates overall (i.e., the southeast) perhaps reflecting differences by race,⁹ educational achievement,¹⁰ rurality,¹¹ and/or cardiovascular morbidities.

Spouses comprise the largest group of caregivers for individuals with ADRD. This is particularly true for veterans with dementia, most of whom are men cared for by their

wives.¹² Decades of research suggests that spousal caregivers are uniquely vulnerable due to increased isolation, older age, and cohabitation status which reduce opportunities for respite.¹³ Couples in which one individual is diagnosed with dementia often experience substantial depression and frustration adjusting to functional changes and losses in roles, relationship, and independence of the declining loved one.¹⁴⁻¹⁶ Changes in shared intimacy, emotional support, companionship, and reciprocity are consequences of memory loss¹⁷ and associated cognitive changes resulting in grief reactions in up to 71% of caregivers.¹⁸ Some research has cited loss of the relationship with the person as the most distressing element of the disease for caregivers and directly predictive of depression above other aspects of the caregiving context.^{14,17} The unique functional and behavioral impairments associated with ADRD contribute substantially to psychological and physical morbidity of family caregivers and high rates of nursing home placement, with 60% of ADRD caregivers rating the emotional stress of caregiving as “high or very high,” and over one third reporting depressive symptoms.

Gaps in Current Knowledge

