10. Number of the subjects that will be recruited for study

At least seventy dyads (i.e. 70 veterans and 70 caregivers) will be recruited to achieve a final sample. However, caregivers can participate independently if the veteran is too impaired to participate meaningfully in the study.

11. Subject inclusion/selection criteria

Veterans:

- a. Must be age 19 or older
- b. Must have a diagnosis of dementia or a related disorder
- c. Must live in the community (i.e. not in a VA Community Living Center, nursing home, or other facility)
- d. Must cohabitatem with a caregiver;
- e. Must have reliable access to a telephone
- f. Must be willing to consent to participate or provide assent in conjunction with proxy consent if their decision-making capacity is compromised.

Caregivers:

- a. Must be age 19 or older
- b. Must self-identify as assisting with care for at least 8 hours/week
- c. Must be willing to consent to participate.

The study will include women and minorities and aim to represent the percentage reflected in Tuscaloosa VAMC medical care system (12% women, 44% minorities, and 1% Hispanic origin; though numbers of minorities might be slightly lower in the older cohorts targeted for this study as indicated above). No specific inclusion/exclusion criteria related to race/ethnicity are required.

12. Subject exclusion criteria

In addition to meeting the inclusion criteria outlined above, participants will be excluded in the following cases.

Veterans:

- a. Currently incarcerated
- b. Currently pregnant
- c. Dyads experiencing low levels of distress (as defined by a score of 0 or 1 on the Dementia Services Mini-Screen³², see below)

Note. Baseline or post-assessment interviews will be discontinued for Veterans experiencing severe cognitive impairment that would impair their ability to communicate during an interview, consistent with good clinical practices. However, they will not be excluded from participating in intervention sessions as appropriate and their available data (self-report or proxy report) will be retained for analyses.

Caregivers:

- a. Currently incarcerated
- b. Currently pregnant
- c. Experiencing severe cognitive impairment that would impair their ability to communicate during an interview
- d. Dyads experiencing low levels of distress (as defined by a score of 0 or 1 on the Dementia Services Mini-Screen³², see below)

13. Subject exit criteria

- a. Subjects will exit the study once one of the following conditions are met:

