r. The 6-item **Desire to Institutionalize (DTI)** Scale⁵¹, which assesses the caregivers planning, thoughts, and actions about long-term care (LTC) placement over the past 6 months will be used to assess intentions to institutionalize their loved one. Six yes/no items (e.g., taken steps toward placement) are summed for a score of 0-6. Long-term care placement and/or hospitalization of the veteran (institutionalization) will be assessed using a single item rated either by the caregiver or via electronic health record review if the dyad is no longer enrolled in the study (e.g., due to attrition).

s. The 21-item **Care Consultation Satisfaction Survey** will be used to measure the participants' satisfaction with the Care Consultant and the Care Consultation services provided.

Once baseline data are collected, dyads will be randomly assigned to a condition (see interventions delivered below).

Randomization

Blocked randomization stratified by race and gender will be used to assign participants to either the: (a) CC group, or the (b) CC+C group. This two-group experimental design was chosen over other approaches (e.g., no comparison group designs, three-group design, cross-over design, etc.) because it most closely approximates the next level of clinical research (e.g., an efficacy study), which allows for the most directly applicable conclusions.

Interventions Delivered

1. Care Consultation (CC): is an established telephone-based, empowerment intervention that uses coaching and emotional support to mobilize family caregivers and individuals with dementia through psychoeducation, resource referral, psychosocial support, and encouragement of informal and formal service use utilization. A computerized clinical tool utilizing a password-protected VA-hosted website (i.e., operated within the VA server system) called the Care Consultation Information System (CCIS) guides the care consultant through a standardized delivery of protocol components, replacing a paper-based clinicians manual. Rather than a strong focus on assessment, this intervention is designed to quickly identify areas of unmet need through brief trigger questions called the “initial assessment” – much like an interview guide – which then immediately shapes development of concrete action plans.

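### The nursing-home placement model has open-ended covariates and no sparse-event method; if placement is around 10% or lower, it has a material chance of giving no finite odds ratio for Group

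*Combined protocol and SAP*

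**What the plan says.** The protocol's Aim 3 (section 6) is exploratory. It predicts that veterans in CC+C will have "lower rates of placement in long-term care facilities at 6 and 12 months than those who receive CC alone". Section 20, Data Analysis, says that "logistic regression analyses will be conducted to determine if NH placement at 6 and 12 months is differentially related to treatment condition", and then: "NH placement (or not) will be the dependent variable in these analyses, and independent variables will include Group and relevant covariates". This is the only analysis named for placement. The covariates are neither listed nor limited in number, and no exact, penalised or unadjusted alternative is given.

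On size, section 20 says: "We plan to recruit at least 70 dyads across the 3-5 year study period to ensure 50 completers at 6 months". Section 11 admits only veterans living in the community, so every event is a new placement. No placement rate is given. The nearest remark is the background's general reference to "high rates of nursing home placement" (section 7).

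Two other places affect the event count:
- Section 17, Measures, item r describes a single item that covers long-term care placement, hospitalization or both. It allows the health record to be used when a dyad has left the study.
- Section 20, Treatment of Missing Values, restricts final analyses to people with at least four sessions and available time 2 data.

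**The concern.** Ordinary logistic regression needs events and non-events in both arms. If one arm has no placements, the likelihood keeps rising as the Group coefficient goes to infinity. Software then prints a very large coefficient with a larger standard error, and the Wald interval means nothing. A covariate category with no events does the same to its own coefficient. The trial is small and the sponsor expects fewer placements in CC+C, so that arm is the more likely to be empty.

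Aim 3's placement result could therefore be missing, most likely at 6 months, when fewer placements will have accrued. With no method stated beforehand, covariates or models would then be chosen after seeing the data. Section 32 says that the study's data will support future grant proposals, so the estimate has a use beyond description.

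**Working it through.** **Inputs from the protocol.** At least 70 dyads are to be recruited, with 50 completers at 6 months (section 20), an implied loss of 1 − 50/70 = 28.6%. The four-session rule would leave roughly 50 veterans, and record review could bring the number to about 70.

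**Assumptions.** Allocation is 1:1, since "Blocked randomization stratified by race and gender will be used to assign participants" gives no ratio. That makes 25 or 35 per arm. CC placement is varied from 5% to 30%. The CC+C rate is either equal to it or has half the odds. The plan has no placement rate, event count or placement power to reproduce; its power inputs are in grant text outside the document.

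**Step 1: chance that at least one arm has no placements.** With n per arm, q1 = (1 − p1)^n and q2 = (1 − p2)^n, and the probability is q1 + q2 − q1·q2.

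- Equal rates of 5%, n = 25: q = 0.95^25 = 0.277, so 2(0.277) − 0.277² = 0.478. With n = 35: q = 0.166, giving 0.305.
- Halved odds, CC at 10%: the odds 0.111 become 0.0556, so p2 = 0.0526. With n = 25: q1 = 0.072 and q2 = 0.259, giving 0.072 + 0.259 − 0.019 = 0.312.

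| CC rate | Expected events, equal rates (n=50 / 70) | Empty arm, equal rates (n=50 / 70) | CC+C rate if odds halved | Empty arm, odds halved (n=50 / 70) |
|---|---|---|---|---|
| 5% | 2.5 / 3.5 | 0.478 / 0.305 | 2.6% | 0.655 / 0.502 |
| 10% | 5 / 7 | 0.138 / 0.049 | 5.3% | 0.312 / 0.172 |
| 15% | 7.5 / 10.5 | 0.034 / 0.007 | 8.1% | 0.136 / 0.055 |
| 20% | 10 / 14 | 0.008 / 0.001 | 11.1% | 0.056 / 0.017 |
| 30% | 15 / 21 | under 0.001 | 17.6% | 0.008 / 0.001 |

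**Step 2: adding covariates.** Trials were simulated with Group, one continuous covariate (log odds ratio 0.5) and one 70/30 binary covariate, with the odds halved in CC+C. Each was checked for separation by linear programming. Some coefficient was not finite in about 80% / 67% of trials (n=50 / 70) at 5% placement, 47% / 33% at 10% and 13% / 5% at 20%, with Monte Carlo error of up to about 1.6 percentage points.

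These counts include trials in which only a covariate's coefficient fails. With equal rates of 10% and five covariates, one of them a category holding 12% of veterans, some coefficient failed in 66% / 49% of trials. The Group coefficient itself failed in only 14% / 5%, as in Step 1.

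**Step 3: when the estimate exists.** Take 20% in both arms with n = 25, so 5 placed and 20 not placed per arm. The standard error of the log odds ratio is √[2(1/5 + 1/20)] = 0.707. The 95% interval multiplies and divides the odds ratio by exp(1.96 × 0.707) = 4.0, so its upper limit is 16 times its lower limit. With Group and five covariates, 10 to 14 events would support six coefficients, or 1.7 to 2.3 events each. Approximate power for 20% against 10% is 0.16 (n=50) or 0.21 (n=70), assuming a two-sided 5% test.

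**The case against.** The strongest objection is that the documents do not show events will be few. They give no rate, and the background's remark on nursing-home placement points away from the 5% row. If the item in section 17 counts hospitalizations, events rise. Seventy dyads is a minimum. Both arms receive active treatment and no effect size is stated, so halved odds is only an illustration. This stands, and it is why every figure above is conditional.

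A reader might infer that the model will often fail whatever the placement rate. The table does not support that: with equal rates of 15% or more, an arm is empty in about 3% of trials or fewer. Nor should the Step 2 any-coefficient figures be read as loss of the treatment comparison, because a failed covariate term can leave the Group estimate finite.

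A reader might also infer that the sponsor has committed to maximum likelihood with several covariates. Section 20 names no estimator and no number of covariates, and an exact or penalised fit would satisfy its wording. The fault is under-specification.

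Finally, the analysis is exploratory, separation is usually visible in the output, and raw counts could still be reported. That limits the harm. It does not supply a method, and the plan does not say that the counts or a risk difference will be reported.

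**Conclusion.** The concern holds conditionally. The chance of no finite Group odds ratio is material if placement is about 5%, whether or not the arms differ. It remains material at about 10%, chiefly if CC+C lowers placement or only about 50 veterans are analysed. At 15-20% or more, or if hospitalizations push events to that level, the estimate will usually exist. It will then be very imprecise and easily overfitted by an open covariate set.

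These conclusions rest on 1:1 allocation, 25 to 35 veterans per arm and assumed placement rates. Aim 3 is exploratory and no stated decision depends on it, so this is a worthwhile tightening of the plan and not a threat to the trial's main comparison.

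**What to change.** In section 20, Data Analysis, replace the placement sentences with the following plan:

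- At 6 and at 12 months, report the number and proportion placed in each arm and the risk difference with a Newcombe or exact 95% confidence interval. This can be calculated even when an arm has no events.
- Include all randomised veterans, using the record review that section 17 already allows after dropout, and do not apply the four-session rule to this outcome. Sparse data alone do not require this, but it keeps events that the rule could discard.
- If a model is fitted, use Firth-penalised or exact logistic regression with Group and at most one covariate named in advance.
- State the expected number of events, and whether hospitalization counts.

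The cost is wording, plus record review for veterans who leave the study. There is less covariate adjustment, and a penalised fit shrinks the odds ratio slightly toward 1. None of this removes the imprecision, which the interval will show.
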